### *Definition of the MACE*

MACE analysis includes:

- All cause death:
  - Cardiac death (in which a direct cause attributable to cardiac disease is present);
  - Sudden cardiac death (in which cardiac death occurred out of the hospital and suddenly; or in the hospital due to ventricular arrhythmias unrelated to other concomitant cardiac conditions);
  - Non-cardiac death (in which the event of death is considered not to be a direct consequence of cardiac disease);
- Hospitalization in which the main diagnosis is myocardial infarction, stroke or heart failure;
- Repeated coronary angiography.

The analysis will consider time to first event and time to each event.

Safety parameters will include data deriving from history and physical examination performed at each visit, laboratory data and results of functional and imaging tests. To enhance detection of adverse events between visits, all patients will be encouraged to contact the research team at any time with concerns or any perceived changes in their healthcare status.

**14. Sample size calculation:** Sample size calculation for the primary endpoint: to detect a mean group difference of change in SAQ score of 9 U, we calculated that a sample size of 70 patients per group (140 patients total) gave 80% power to detect a between-group difference in SAQ. This

calculation assumed a 2-tailed 5% significance level. This projected calculation assumed an SD of 19 U and was consistent with previous studies (see landmark CorMicA trial). However, we extended the sample size at 180 patients to avoid any reduction of statistical power due to patients lost at follow-up or due to poor compliance to medical therapy.

**15. Timeline:** At 36 months all patients will be enrolled and will have completed the follow-up. The study will be considered ended after the date of last patient last visit (LPLV). Blood samples will be analysed for assessment of circulating biomarkers and miRNA to detect associations with specific mechanisms underlying MINOCA, for stratification of prognosis and to evaluate response to medical therapy. Furthermore, CMR sequences will be analysed to detect functional and structural characteristics associated with specific mechanisms underlying MINOCA and with for stratification of prognosis.

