### **11a. Intervention(s):**

Patients with myocardial infarction undergoing to clinically indicated coronary angiography will be asked to sign the informed consent to the study before the coronary angiography/ventriculography and enrolled only after MINOCA diagnosis. MINOCA patients will be then randomized 1:1 (using an online software available 24h/24h) to:

**A. "Precision medicine approach"** consisting of:

*Comprehensive diagnostic work-up with:*

- Coronary angiography and ventriculography in all patients
- OCT (if coronary plaque rupture/erosion is suspected) at the time of coronary angiography in the cath-lab.
- Acetylcholine provocative test (to assess the presence of coronary vasospasm) at the time of coronary angiography in the cath-lab.
- TE-Echo and/or CE-Echo (if distal/microvascular embolization is suspected) during the hospitalization at the echo laboratory
- Blood sampling for circulating biomarkers and miRNA expression profile at the time of coronary angiography or within 12 hours from coronary angiography. Blood sampling will be processed and analysed in the research laboratory of the Department of Cardiovascular Science. Biological aliquots will be preserved at XBiogem Biobank at Fondazione Policlinico Universitario A. Gemelli IRCCS, Rome.
- Trans-thoracic echocardiography in all patients during the index hospitalization
- CMR in all cases during the index hospitalization.

*Targeted pharmacological treatment specific for the underlying cause:*

- DAPT ± stent implantation (if required), statins, beta-blockers, ACEi/ARB (in case of evidence of plaque rupture/erosion)
- CCB and/or nitrates (in case of documentation of coronary vasospasm)
- Anticoagulation (in case of coronary embolism).

**B. "Standard approach"** consisting of:

*Routine diagnostic work-up with:*

- Coronary angiography and ventriculography
- Transthoracic echocardiography in all patients during the index hospitalization
- CMR with contrast media only if clinically indicated (i.e. to exclude myocarditis or takotsubo syndrome)

*Standard medical treatment with:*

- DAPT in all patients
- Beta-blockers (if indicated by the clinical context, i.e. documentation of left ventricular ejection fraction <50%, tachycardia).

- High intensity statins in all patients
- ACEi/ARB (if clinically indicated).

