## **12. Outcomes of interests:**

Primary endpoints:

- Angina status and quality of life (evaluated using the Seattle Angina Questionnaire [SAQ]) at 1-year follow-up in patients with MINOCA.

[figure not shown]
\* To reduce the risk of detection and performance bias, a team of 2 cardiologists blinded to group allocation and belonging to an external cardiology unit will submit and collate the questionnaires from study participants.

Secondary endpoints:

- Rates of major adverse cardiovascular events (MACE; composite of all-cause mortality; re-hospitalization for myocardial infarction, stroke or heart failure; repeated coronary angiography) at 1-year follow-up in MINOCA patients.
- Healthcare primary and secondary related-costs (including costs for tests, procedures and outpatient visits or medicines) and socioeconomic burden of MINOCA patients.
- Ability of different circulating biomarkers (ET-1, NPY, CRP, sCD40L and miRNA [miR-16, miR-26a, miR-145, miR-222, miR-155-5p, miR-483-5p and miR-451]) as diagnostic biomarker and stratification tool for specific causes of MINOCA.
- Ability of CMR in evaluating different mechanisms of MINOCA and their prognostic value.

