***T4\_ Follow-up clinical visit at 12 months (365 +/- 5 gg)***

- Personal information: weight, height, BMI
- Collection of ongoing medical therapy
- Compilation of SAQ score
- Collection of MACE at follow-up
- Registration of adverse events

Study Assessment	Screening and randomization	Follow-up phone interview_ T1 (3 months)	Follow-up phone interview_ T2 (6 months)	Follow-up phone interview_ T3 (9 months)	Visit of End of Follow-up (12 months)
Days	0	90 +/- 5 gg	180 +/- 5 gg	270 +/- 5 gg	365 +/- 5 gg
Weeks	0	12	24	36	52

Informed consent	X				
Inclusion criteria	X				
Anagraphic data	X				
Personal information (weight, height,BMI)	X				X
Clinical history	X				
Clinical examination	X				
Vital signs	X				
Ongoing medical therapy (concomitant medications included)	X	X	X	X	X
Patients assigned to "Standard approach"	X				
ECG features	X				
Transthoracic Echocardiography	X				
Coronary angiography and ventriculography	X				
CMR with contrast media (if clinically indicated)	X				
Laboratory data (creatinine, full blood count, Troponin I peak, CK-MB peak, NTproBNP, CRP)	X				
Patients assigned to "Precision-medicine approach"					
OCT (if coronary plaque rupture/erosion is suspected)	X				
	X				

Acetylcholine provocative test (to assess the presence of coronary vasospasm)					
TE-Echo and/or CE-Echo (if distal/microvascular embolization is suspected)	X				
CMR with contrast media (if clinically indicated)	X				
Blood sampling for circulating biomarkers and miRNA expression profile	X				
Collection of MACE	X	X	X	X	X
Adverse events	X	X	X	X	X
SAQ score					X

SAQ score:

1. The following is a list of activities that people often do during the week. Although for some people with several medical problems it is difficult to determine what it is that limits them, please go over the activities listed below and indicate how much limitation you have had **due to chest pain, chest tightness, or angina over the past 4 weeks.**

Place an x in one box on each line.

Activity	Severely Limited	Moderately Limited	Somewhat Limited	A Little Limited	Not Limited	Limited, or did not do for other reasons
Dressing yourself						

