## **METHODS: INTERVENTION ALLOCATION**

### **16-17 Randomization**

Trained staff in the catheter laboratory will use a web-based randomization tool, available 24h/24h at any of the enrolling sites, to immediately randomize the patient after the index coronary angiography revealing non obstructive CAD, to “precision medicine approach” versus “standard approach” (open label approach: both patients and physicians will know the allocated treatment arm).

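### MACE has two non-equivalent definitions, and under either one a non-fatal MI, stroke or heart failure between randomisation and discharge is not counted unless it leads to a repeat angiogram

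*Combined protocol and SAP*

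**What the plan says.** Section 12 lists MACE as a secondary endpoint: all-cause mortality, then "re-hospitalization for myocardial infarction, stroke or heart failure; repeated coronary angiography) at 1-year follow-up in MINOCA patients". The section headed Definition of the MACE gives the non-fatal clinical component as "Hospitalization in which the main diagnosis is myocardial infarction, stroke or heart failure", with all-cause death and repeated coronary angiography as the other components. It adds: "The analysis will consider time to first event and time to each event". It states no time origin and does not exclude the admission that qualified the patient for the trial.

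On timing, section 16-17 has catheter-laboratory staff use a web tool "to immediately randomize the patient after the index coronary angiography revealing non obstructive CAD". Section 11a then gives the precision arm "Acetylcholine provocative test (to assess the presence of coronary vasospasm) at the time of coronary angiography in the cath-lab". The same arm has OCT at the angiogram if plaque rupture or erosion is suspected, and transoesophageal or contrast echo during the stay if embolisation is suspected. Stent implantation, if required, appears under that arm's treatment. The standard arm's work-up contains none of these added tests. The study assessment table ticks "Collection of MACE" in every column, including the day 0 column for screening and randomisation.

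**The concern.** The two definitions describe different events, and neither makes an MI, stroke or heart failure episode an event in its own right. Each needs a hospitalisation to carry it. During the index stay the patient is already in hospital, so a non-fatal event before discharge has nothing to attach to. That is the window in which the trial's extra invasive procedures take place, and they take place in one arm.

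Prognosis is the first secondary objective in section 7, and MACE is the endpoint that addresses it. A composite that counts later benefit but omits early non-fatal procedural harm cannot show the net effect of the strategy. Without a time origin, the planned time-to-event analysis also leaves open whether the clock starts at admission, randomisation or discharge.

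**Working it through.** **The plan's own figures.** The documents give no MACE rate, power or complication rate, so there is no MACE figure to reproduce. The sample size in section 14 concerns SAQ and does not bear on this point. The main check is to apply each definition to each type of event.

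| Event after randomisation | Section 12 (re-hospitalisation) | Definition of the MACE (hospitalisation by main diagnosis) |
|---|---|---|
| Death in the index stay | counts | counts |
| Repeat angiogram in the index stay | can count, under its own component | can count, under its own component |
| Non-fatal stroke or heart failure before discharge, no repeat angiogram | no: not a re-hospitalisation | no: no new admission, and the main diagnosis of the current one would normally be the qualifying MI |
| Non-fatal new MI before discharge, no repeat angiogram | no: not a re-hospitalisation | adds nothing: no new admission, and this one is already an MI admission |
| The qualifying admission itself | no | not excluded by the wording |
| Admission for MI, stroke or heart failure after discharge | counts | counts if it is the main diagnosis |

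The day 0 tick in the schedule shows that MACE is meant to be collected from the start, yet neither definition lets the events in rows 3 and 4 be recorded.

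**Illustration of size.** Inputs:

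- 90 patients per arm, from 180 randomised 1:1 (sections 8 and 14).
- 9 later events per arm (90 × 10%): assumption.
- In-hospital MI, stroke or heart failure after randomisation of 1-3% in the precision arm and 0-1% in the standard arm: assumption. The risk analysis calls complications of OCT and acetylcholine testing rare but gives no rate.

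Uncounted events are 90 × 1% = 0.9, about 1, to 90 × 3% = 2.7, about 3, in the precision arm. In the standard arm they are 0 to about 1. As counted, the comparison is 9 v 9, a relative risk (RR) of 1.0. With index-stay events added:

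| Precision / standard in-hospital rate | Events | RR |
|---|---|---|
| 1% / 1% | 10 v 10 | 10/10 = 1.00 |
| 1% / 0% | 10 v 9 | 10/9 = 1.11 |
| 3% / 1% | 12 v 10 | 12/10 = 1.20 |
| 3% / 0% | 12 v 9 | 12/9 = 1.33 |

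For the extreme row, SE(log RR) = √(1/12 − 1/90 + 1/9 − 1/90) = 0.415. The 95% interval is exp(ln 1.333 ± 1.96 × 0.415) = 0.59 to 3.01, and Fisher's exact p = 0.64.

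These figures assume that none of the added events led to a repeat angiogram. Any that did would be counted already, and the shift would be smaller.

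**The case against.** The strongest case on the other side is that this is a wording mismatch in an unpowered secondary endpoint.

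- **Repeat angiography catches some events.** It is a separate component with no re-hospitalisation condition, so a coronary complication that sends the patient back for angiography can count. This stands. It would be wrong to infer that an in-hospital event counts only if fatal.
- **The qualifying MI would not be scored.** A reader might infer from the Definition of the MACE that all 180 patients have an event at entry and that time to first event is meaningless. The documents do not support that: section 12 says re-hospitalisation, and the follow-up visits collect MACE at follow-up. The missing exclusion is a drafting gap, not a likely analysis.
- **The bias is not shown.** A reader might infer that the comparison is certainly tilted towards the precision arm. Only harm from the added tests is confined to that arm. Treatment starts during the index stay in both arms, so early recurrent events can also go uncounted in controls.
- **Safety reporting covers these events.** Adverse events are collected from day 0, and an event that prolongs the stay is serious under section 22. This stands as regards patient safety, but it does not bring the events into the MACE comparison.
- **Counting early MI is difficult.** Angiography is planned within 90 minutes or 48 hours of admission, while the qualifying MI is still acute. Treatment is open label and no MACE adjudication is described. A main-diagnosis requirement limits subjective calls. This stands too, and the fix has to deal with it.

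**Conclusion.** The concern holds in a limited form. The two MACE definitions conflict, the time origin is missing, and both wordings leave out non-fatal MI, stroke and heart failure between randomisation and discharge unless a repeat angiogram follows. None of this depends on any assumed rate.

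Omitting complications of the added tests would favour the precision arm. The size and net direction of the effect on MACE are unknown. Under the assumed rates, a true RR anywhere from 1.0 to 1.33 would appear as 1.0. Even the extreme is far from significant, so the issue is incomplete accounting of the strategy's effect and not a likely reversal of a trial conclusion. MACE is secondary, most of the missed events would be reported as serious adverse events, and the primary SAQ result is unaffected. The sponsor should correct it, but it does not threaten the trial.

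**What to change.** Use the same definition in section 12 and in Definition of the MACE: all-cause death; MI, stroke or heart failure with onset after randomisation, whether during the index stay or leading to re-hospitalisation; and repeated coronary angiography. With it:

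- State that the clock starts at randomisation.
- State that the qualifying MI and its admission are not events.
- State that study-mandated angiograms during acetylcholine testing are not repeated coronary angiography. Without this, the protocol's own imaging after each injection could be read as an event in the precision arm.
- Pre-specify how a new MI is recognised when troponin is already raised.
- Report index-stay events by arm on a separate line, and give MACE excluding the index stay as a sensitivity analysis.

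The cost is protocol wording and a small eCRF change; MACE and adverse events are already collected at day 0. The drawbacks are some subjectivity in classifying early MI in an open-label trial, which the sensitivity analysis would expose, and a possibly slightly less favourable count in the precision arm.

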***T1\_ Follow-up phone interview at 3 months (90 +/- 5 gg)***

- Collection of MACE at follow-up
- Collection of ongoing medical therapy
- Registration of adverse events

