## **METHODS: DATA COLLECTION, MANAGEMENT AND ANALYSIS**

**18. Data collection:** Data collection will be carried out through an electronic CRF (eCRF). The investigator or an authorized member of the investigation team must sign all completed eCRFs with a digital signature (a password will be provided by the data management center at the start of the study). The management of clinical data will be carried out in accordance with the data cleaning procedures, both for the data recorded in the eCRFs and from other sources. Appropriate computerized software will be used to verify the accuracy of the database. Investigators will be asked for incomplete, inconsistent or missing data.

**Source Documents (SDs):** Investigators have to maintain information in the patient's medical record that corroborates the data collected in the eCRF. To meet these demands, the following is a list of information that must be recorded and shown to monitors and regulatory inspectors as needed: Clinical history / physical condition of the participant before inclusion in the study with sufficient detail to verify the inclusion and exclusion criteria; clinical notes dated and signed on the day of entry into the study, protocol number, clinical site, number assigned to the patient and a declaration certifying the signature of the informed consent; record of abnormal laboratory tests; reported adverse events and their resolution; including supporting documents such as discharge sheet, catheterization reports, ECG, echocardiography and CMR reports; laboratory results; condition of the patient upon completion or withdrawal from the study.

**Case Report Form:** All requested data will be carefully recorded by authorized personnel documented in the Authorized signature log in the eCRF.

**19. Confidentiality:** All data and information collected during this study concerning the participant must adhere to the privacy protection standards, based on the application of the Italian laws on the

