### **Data Monitoring Committee (DMC)**

The DMC will consist of an independent group of 3 experts consisting of a clinical cardiologist expert in cardiovascular emergencies, an interventional cardiologist, and a clinical cardiologist expert in biostatistics. The DMC has experience in managing acute patients undergoing coronary revascularization and conducting a clinical trial. The DMC is responsible for monitoring the safety of participants and the conduct of the PROMISE trial. The DMC provides recommendations on the advisability of continuing the clinical trial or of adopting protocol changes necessary to maintain the safety of enrolled patients. The composition of the DMC will be defined before the start of the clinical trial. The initial DMC meeting will occur at the start of the trial and will convene once annually, to

examine the accumulated safety and enrollment data, review study progress, and discuss all the factors that might impact continuation of the study as designed.

**21.** It is the responsibility of the PI to report any changes in the research activity and unanticipated problems concerning the risk to human beings; including planned or untimely conclusion of the study and final report. Premature interruption of the study must be reported within 15 days. The regular term of the study will be communicated to AIFA (OsSC) and the CEC within 90 days. The final study report will be reported within 1 year of the end of the study.

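### MACE counts any repeat coronary angiography in an open-label trial, and no analysis without that component is pre-specified

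*Combined protocol and SAP*

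**What the plan says.** Section 12 lists MACE as a secondary endpoint: death from any cause, rehospitalization for myocardial infarction, stroke or heart failure, and "repeated coronary angiography) at 1-year follow-up in MINOCA patients". The MACE definition in section 13 repeats the last component simply as "Repeated coronary angiography". The hospitalization component does carry a qualifier there, because the main diagnosis must be one of three conditions. The angiography component carries none.

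Sections 16-17 describe the trial as "open label approach: both patients and physicians will know the allocated treatment arm". Under section 11a, acetylcholine testing and, where plaque rupture or erosion is suspected, OCT are done at the index angiogram in the precision arm only. The standard arm has angiography, ventriculography, echocardiography, and CMR if clinically indicated.

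The schedule in section 13 lists "Collection of MACE at follow-up" at the telephone interviews at 3, 6 and 9 months and again at the 12-month visit, without saying who collects it. Section 18 states: "The investigator or an authorized member of the investigation team must sign all completed eCRFs". The only blinded assessors are "a team of 2 cardiologists blinded to group allocation and belonging to an external cardiology unit", who "will submit and collate the questionnaires from study participants". On the monitoring committee the protocol says: "The DMC is responsible for monitoring the safety of participants and the conduct of the PROMISE trial". It gives that committee no role in classifying events.

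**The concern.** Repeat angiography is something a doctor decides to do, and the protocol gives no criteria for it. The doctor knows the arm, and the arms differ in what is known after the index procedure. A standard-arm patient with recurrent chest pain has had no acetylcholine test or OCT under the protocol, and either would need another catheter-laboratory procedure. In a precision-arm patient the mechanism may already be established. So the component may partly record whether mechanism testing was done at time zero, which is the randomized difference itself.

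The opposite direction is also possible. A mechanism found in the precision arm could prompt a further procedure, and a planned second angiogram in either arm would count as an event.

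What is at stake is the claim about prognosis. Section 8 describes a trial of prognosis and/or quality of life, prognosis is the first secondary objective in section 7, and MACE is the endpoint that would carry it. A difference in MACE could be read as fewer deaths and serious admissions when it reflects only how often doctors chose to look again.

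**Working it through.** **The plan's own figure.** The only sample size calculation is for the SAQ (section 14): difference 9, SD 19, two-sided 5%, 80% power. Per group, n = 2 × (1.960 + 0.842)² × 19² / 9² = 70, as stated. The total is extended to 180, which is 90 per arm at 1:1. No event rate or power is given for MACE, so everything below rests on assumed rates.

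**Set-up.** Let h be the proportion with death or hospitalization for infarction, stroke or heart failure (the hard events), equal in both arms, so that there is no true effect on them. Let a be the proportion with repeat angiography. Assuming the two are independent, the composite proportion is 1 − (1 − h)(1 − a). The test is the two-sided Fisher exact test, which section 20 names for categorical outcomes. The chance of p≤0.05 was found by enumerating all outcomes with 90 per arm.

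**Main illustration, h = 12% in both arms**

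| Repeat angiography, precision vs standard | Composite, precision | Composite, standard | Relative risk | Chance of p≤0.05 |
|---|---|---|---|---|
| 5% vs 5% | 1 − 0.88 × 0.95 = 16.4% | 16.4% | 1.00 | 3% |
| 5% vs 8% | 16.4% | 1 − 0.88 × 0.92 = 19.0% | 0.86 | 5% |
| 5% vs 10% | 16.4% | 1 − 0.88 × 0.90 = 20.8% | 0.79 | 8% |
| 5% vs 13% | 16.4% | 1 − 0.88 × 0.87 = 23.4% | 0.70 | 17% |
| 3% vs 18% | 1 − 0.88 × 0.97 = 14.6% | 1 − 0.88 × 0.82 = 27.8% | 0.53 | 52% |

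With the arms exchanged, the chance of p≤0.05 is the same and the relative risk is inverted: 13% vs 5% gives 0.234/0.164 = 1.43.

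**Other hard-event rates, precision-arm repeat angiography 5%**

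| Standard-arm repeat angiography | Chance of p≤0.05, h = 5% | Chance of p≤0.05, h = 10% |
|---|---|---|
| 10% | 12% | 9% |
| 15% | 37% | 27% |
| 20% | 67% | 54% |

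At 20% the apparent relative risk is 0.41 (h = 5%) or 0.52 (h = 10%), again with no difference in hard events.

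**Power of the analysis without angiography.** If the precision approach truly halved hard events from 12% to 6%, Fisher's test with 90 per arm would give p≤0.05 about 22% of the time.

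**The case against.** The strongest reply is that MACE is secondary and unpowered, that no passage shows referral will differ, and that a moderate imbalance seldom produces significance: about 8% of trials at 5% vs 10%, against 3% with no imbalance. All of that stands. The large figure needs a six-fold gap in referral. But a relative risk of 0.70 reported without its components can mislead even when it is not significant.

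A second reply is that section 13 already plans to look at the timing of each event as well as the first. That can be read as an analysis by component, which narrows the gap. It does not supply the composite without angiography, and section 20 does not mention it.

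Several stronger readings are tempting, and the documents do not support them:

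- That unblinded staff collect MACE. The collector is not named; the text says only who signs the eCRF.
- That the standard arm's cause is never investigated. That arm has a routine work-up, though a less extensive one.
- That the bias must favour the precision arm. The direction is unknown.
- That the two blinded SAQ cardiologists could remedy this by classifying events. Masked reading cannot blind the decision to refer, and with no definition of a qualifying angiogram a reader could only confirm that one took place. Reading catheterization and discharge records from month 3 could also unmask them before the 12-month SAQ, and the files would need redaction.

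**Conclusion.** The point holds in a limited form. Counting every repeat angiogram, in an open-label trial whose arms differ in invasive testing at the index procedure, lets the composite differ by arm with no difference in death or serious admission. Nothing in the plan separates the two. With hard events assumed equal at 12% and the components independent, the spurious relative risk runs from 0.79 (5% vs 10%) to 0.53 (3% vs 18%), and the chance of p≤0.05 from about 8% to about 52%. These are illustrations, not predictions, because the documents give no rates.

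A reader might infer that the trial's main result is compromised. It is not: the primary SAQ conclusion and the sample size do not depend on MACE. What needs protecting is any statement about prognosis.

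**What to change.** Keep the composite as defined. In section 20, pre-specify three things before outcomes are compared by arm:

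1. Alongside MACE, the same analysis of death from any cause or hospitalization for myocardial infarction, stroke or heart failure, leaving out repeat angiography.
2. The number and proportion of patients with each component, by arm.
3. A sentence stating that a MACE difference driven only by repeat angiography will not be described as improved prognosis.

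The cost is one extra analysis and one table, on data already collected, with no change to visits, sample size or treatment. The drawback is that the supportive analysis has fewer events and low power (about 22% for a halving from 12% to 6%). It guards against over-claiming and should not be a significance gate: a rule that both analyses must reach significance would fail most of the time even if a benefit of that size were real. The blinded SAQ cardiologists should keep to the questionnaires.
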